4.2.3 Observational Assessments

The following observational assessments will be performed and/or summarized:

- Comparison of EchoSure and duplex measurements of flow, diameter, and depth. Only duplex images that pass a quality control check by an Independent RVT will be included in the assessment.
- Comparison of EchoSure depth measurements to Independent Reviewer measured depth results.

- Time to radiographic maturation is defined as the number of days from baseline procedure to date of radiographic maturation (date of ultrasound imaging, as adjudicated by the CEC). Radiographic maturation is defined as a fistula with volume flow of 500mL/min and 5mm diameter.
- Time to clinical maturation defined as the number of days from baseline procedure to date of clinical maturation. Clinical maturation is defined as 75% of dialysis sessions with successful 2 needle cannulation for 4 weeks. Date of clinical maturation is defined as first date of the 4-week window when clinical maturation is achieved.
- Radiographic maturation success rate defined as the percentage of subjects that achieve radiographic maturation (as determined by the physician and adjudicated by the CEC) by end of study. Radiographic maturation is defined as a fistula with volume flow of 500mL/min and 5mm diameter.
- Clinical maturation success rate is defined as the percentage of subjects that achieve clinical maturation by end of study. Date of clinical maturation is defined as first date of the 4-week window when clinical maturation is achieved.
- 6-month patency rate as defined by the status (yes/no) of an arteriovenous dialysis access with detectable blood flow through and beyond the anastomosis shown by either an imaging modality or physical examination (presence of a palpable thrill or audible bruit along some point of the arteriovenous dialysis access beyond the arteriovenous anastomosis). ⁸
- 12-month patency rate as defined by the status (yes/no) of an arteriovenous dialysis access with detectable blood flow through and beyond the anastomosis shown by either an imaging modality or physical examination (presence of a palpable thrill or audible bruit along some point of the arteriovenous dialysis access beyond the arteriovenous anastomosis).
- Occurrence of events occurring within 30 days of implantation that require reinterventions (open or endovascular), hospitalizations, or prolongation of existing hospitalization.
- Occurrence of reported reduction of blood flow that prevents the ability to cannulate or requires further assessment and/or intervention from baseline procedure to 12 months.
- Occurrence of the reported inability to cannulate fistula beginning once the fistula is deemed radiographically and clinically mature to 12 months.
- Occurrence of the development of steal syndrome from baseline to 12 months.
- Occurrence of bleeding requiring surgical intervention (including PRBC transfusion) from baseline to 12 months.
- Occurrence of infiltration requiring procedural intervention from baseline to 12 months.

- Occurrence of hematoma requiring procedural intervention from baseline to 12 months.
- Occurrence of the inability to use the EchoSure component of the system, from baseline to 4 months, due to:
 - Migration of the EchoMark device
 - Early resorption of the EchoMark device as defined as breakdown of the EchoMark shape prior to 4 months from index procedure.
 - EchoMark will continue to be monitored throughout the duration of the study.
- Occurrence of pain associated with the study devices from baseline to 12 months.
- Occurrence of infection (not limited to infection requiring implant explantation) from baseline to 12 months.
- Occurrence of infection confirmed by either implant explanation or purulent fluid on pathologic assessment during incision and drainage from baseline to 12 months.
- Composite of new major device related adverse events (MAEs) at 12 months post EchoMark LP implantation, as adjudicated by the Clinical Events Committee (CEC). The proportion of subjects with device success and free from device- and/or procedure-related SAEs (per CEC adjudication) at 12 months. The summaries for each individual safety data point will also be provided, including:
 - Device or procedure-related death
 - Device related infection
 - Device related interventions
 - Device related hospitalizations
 - o Fistula failure
 - Fistula rupture
 - o Aneurysm

5. STUDY DESIGN

5.1 Overall Design

This is a prospective, multi-center, single-arm, non-blinded clinical trial designed to evaluate the feasibility and safety of the Sonavex EchoMark and the EchoSure in subjects undergoing new upper arm autologous arteriovenous fistula creation who require hemodialysis. The trial will enroll up to 20 subjects in up to 6 clinical sites in the United States. Each site can enroll up to 3 "roll-in" subjects. Roll-in subjects will be consecutive, must be identified as roll-in subjects prior to the EchoMark implantation, and will not count toward the total enrollment of 20 subjects.

5.2 Blinding

The data from EchoSure will not be used in clinical care. The study investigators will be blinded to EchoSure results and comparison of EchoSure measurements to Duplex measurements until the end of the study.

5.3 End of Study

All enrolled subjects will exit the study when all study related activities and visits are completed, but no later than 24 months.

6. STUDY POPULATION

6.1 Clinical Sites

It is important to select the appropriate clinical sites for this trial. Investigators should be credible and experienced, and the sites should experience a high enough volume of subjects undergoing upper arm autologous arteriovenous fistula creation for hemodialysis.

It is estimated that up to 6 clinical sites including hospitals and surgical centers in the United States will enroll in this trial. All follow up visits included in this study where the EchoSure device is used will be conducted at the vascular surgeon's office/clinic.

6.2 Determination of Study Eligibility

All subjects will be required to sign the Institutional Review Board–approved informed consent form for the study.

Upon satisfying inclusion and exclusion criteria, a clinical history and signing the informed consent form, a subject will be eligible for enrollment in the trial.

6.3 Inclusion Criteria

Subjects will be included if all the following inclusion criteria apply:

- 1. Males or non-pregnant, non-breastfeeding females ≥ 18 years of age but < 85 years of age at the time of informed consent
- 2. Subject is able and willing to provide written informed consent prior to receiving any non-standard of care, protocol specific procedures
- 3. Subject is willing and capable of complying with all required follow-up visits
- 4. Subject and/or Care Team agree that the distance and transportation resources from the subject's home to the clinic are reasonable for study participation and compliance
- 5. Subject has an estimated life expectancy > 18 months
- 6. Subject is ambulatory (cane or walker are acceptable)
- 7. Subjects presenting for upper arm autologous arteriovenous fistula creation
- 8. Vein diameter > 2.5 mm at the antecubital fossa via imaging
- 9. Artery diameter > 3 mm via imaging

10. Subject is not participating in another investigational clinical trial that has not met its primary endpoint. Participation in a post-market registry is acceptable.

6.4 Exclusion Criteria

Subjects will be excluded if any of the following exclusion criteria apply:

- 1. Subjects receiving a forearm fistula.
- 2. Subject has history of Steal Syndrome.
- 3. Subject who is immunocompromised or immunosuppressed.
- 4. Subject has had three previous failed AV fistulae for hemodialysis access
- 5. Subjects expecting to undergo major surgery within 60 days from the EchoMark implantation.
- 6. Known or suspected active infection on the day of the index procedure.
- 7. Subjects who had infection(s) in the 30-day window prior to EchoMark placement to reduce the likelihood of partially treated infections that can seed the device and fistula
- Subjects with diagnosed bleeding disorder, thrombocytopenia (platelet count <50,000), hypercoagulability, and history of recurrent deep vein thrombosis not related to AV access
- 9. Subjects with active malignancy
- 10. Subjects with a history of poor compliance with the dialysis protocol
- 11. Subjects with a known or suspected allergy to any of the device materials
- 12. Subjects with an existing fistula or graft
- 13. Subjects who are pregnant, plan to become pregnant, or are breastfeeding.

6.5 Strategies for Recruitment and Retention

The clinical research personnel will screen and attempt to enroll subjects in clinical settings scheduled for an upper arm autologous arteriovenous fistula creation who meet the study criteria. Qualified research personnel will be responsible for obtaining informed consent. The prospective participants will be informed the study is solely voluntary and that they can choose to not enroll or exit the study at any time without consequence to the quality of their care or services provided. Prospective participants will be provided with adequate time to make an informed decision and will be invited to ask questions.

6.6 Screen Failures

Screen failures are defined as subjects who consent to participate in the clinical trial but never have the EchoMark implanted. A minimum set of screen failure information is required including demographics, screen failure details, and eligibility criteria. Screen failures can be replaced.

7. STUDY INTERVENTION

7.1 EchoSure Scan Requirements

The EchoSure scans will be conducted at the vascular surgeon's (investigator's) office/clinic by a member of their staff that does not have formal ultrasound training and has been designated and trained as study personnel. Appropriate staff members to conduct the EchoSure scans include the study research coordinator(s), nurses, nursing assistants, or medical technicians. Prior to starting study activities, each site will designate at least one staff member without previous ultrasound training to conduct the EchoSure scans. These designated EchoSure users will be trained on the use of the EchoSure system and how to fill out the EchoSure case report form, including the blinding of the investigator, during Site Initiation Visits. The designated EchoSure users will be included in the study delegation log of authority and a copy their CV/resume will be included in the site's study regulatory binder. No other study personnel will operate the EchoSure system.

The follow-up EchoSure scans will be conducted by the designated EchoSure user without the investigator and without the sonographer/RVT conducting the Duplex exam in the room, either during the routine work-up prior to the surgeon seeing the patient or after. The EchoSure results for flow, and vessel depth and diameter are shown as numerical values on the screen of the EchoSure device. After each scan, the EchoSure user will transcribe these values onto the case report form. The EchoSure data will not be included elsewhere in the patient's medical record. The CRF data will be entered in to an EchoSure master data spreadsheet by a data manager. This master data spreadsheet will not be available to investigators. While historical EchoSure scans and data are stored on the EchoSure users will be given login credentials. The investigator's will not be provided with login credentials, so they will not be able to log in to the system to conduct EchoSure scans or view any of the EchoSure measurement data.

7.2 Duplex Scan Requirements

The Duplex exams will be conducted by certified sonographers or registered vascular technologists (RVT), or physicians experienced in vascular ultrasound exams who have been trained on the study's Duplex data collection protocol (defined in Section 7.4, pg 36 – 39, of the Investigator's Brochure). All study personnel will be instructed during training that the sonographer/RVT must not be in the room during the EchoSure scans. During the Duplex exam, the sonographer/RVT will fill out the Duplex Follow-Up CRF which includes transcribing the numerical values for flow and vessel depth and diameter that result from the Duplex exam. The saved Duplex data (specific images with caliper measurements and calculations as outlined in the study Duplex protocol) and the CRF will be sent to an Independent RVT for quality checks. An Independent RVT will verify the quality of Duplex images and measurements following defined specifications and key-in verified numerical values for flow and vessel depth and diameter. This master data spreadsheet will not be available to the investigators.

7.3 Pre-Procedure Requirements

Once informed consent is obtained the subject is enrolled in the study. The subject will undergo the following procedures:

- Demographics
- Vital Signs
- Medical History to include the most recent Kt/V, CBC, Serum Chemistry, Calcium, Phosphorous, Magnesium, Total Protein, Albumin, PTH
- Relevant medications
- Duplex scan to assess the blood flow, depth and diameter of the target vessels.
- Duplex scan to assess the Brachial Artery for flow and diameter.
- Blood culture to confirm absence of bacteremia.

7.4 Study Procedure

All subjects will undergo a physician exam prior to their arteriovenous fistula creation per the institution's standard of care. After the fistula creation is completed, but prior to closure, the EchoMark will be implanted under the outflow vein and secured in place using 3-0 or 4-0 Prolene or equivalent non-resorbable sutures. The EchoMark is to be secured a minimum of 3 cm away from the anastomosis. Procedure details and outcomes will be collected, including:

- Inflow Artery Diameter
- Outflow Vein Diameter
- Length of vessel from anastomosis to the closest edge of the EchoMark
- Adverse Events
- Procedure Success

7.5 Post-Procedure Through Discharge

Subjects will be followed through discharge. The subject will be evaluated for flow by physical exam to include assessment of palpable thrill and audible bruit and will be monitored for adverse events. The subject will undergo a duplex scan, capturing the flow rate, diameter, and depth when feasible. Additionally, an external measurement of each EchoMark corner location will be completed. The EchoMark will be located with palpitation and each corner will be measured independently to the antecubital fossa.

7.6 Pre-Maturation Follow-up at 15, 30, 60, 90, 120, 150 Days

Subjects will have follow-up visits at 15 (+/- 7 days), 30 (+/- 7 days), 60 (+/- 15 days), 90 (+/- 15 days), 120 (+/- 15 days), and 150 (+/- 15 days) days from the baseline procedure, including a physical exam, duplex imaging, EchoSure scan, external EchoMark measurement, medical history, and adverse event monitoring. The EchoSure scans will be suspended after the 120 day (4 month) visit or once radiographic maturation is achieved,

whichever is longer. Radiographic maturation is defined as 500mL/min and a 5 mm diameter. The monthly clinical follow-up and duplex imaging will continue per the follow-up schedule. The physical exam will include assessing the fistula for bruit and thrill. The medical history will include all interventions, cannulation history including any attempts, and the most recent Kt/V, CBC, Serum Chemistry, Calcium, Phosphorous, Magnesium, Total Protein, Albumin, PTH. EchoSure scans will be completed by study personnel who do not have prior ultrasound training, are representative of non-expert users, and have been delegated on the delegation of authority log. Duplex and EchoSure scans will include:

- A total of three (3) EchoSure scans performed at the site of the EchoMark. Volume flow, diameter, and depth data to be recorded.
- A total of three (3) limited DUS scans performed at the site of the EchoMark. DUS will be performed in transverse Bmode and longitudinal view. Volume flow, diameter, depth, and distance from scan area to anastomosis will be recorded.
- A total of three (3) limited DUS scans performed at the cannulation zone in transverse Bmode and longitudinal view. Volume flow, diameter, and depth, will be recorded.
- The 9 Duplex images will be de-identified and undergo quality control checks performed by an Independent RVT.
- A duplex exam of the fistula from the EchoMark location and beyond to assess for the presence of stenotic lesions. If a lesion is present, capture and save an image showing a longitudinal view of the fistula segment with the stenosis, note the location of the stenosis in relation to the anastomosis and EchoMark, and track the stenosis as an adverse event.
- A duplex scan of the brachial artery to assess flow and diameter, capture a PW image showing the flow and diameter measurements.

7.7 Post-Maturation Follow-up at 150 Days if Radiographic Mature

The EchoSure scans will be suspended after the 120 day (4 month) visit or once radiographic maturation is achieved, whichever is longer. Radiographic maturation is defined as fistula diameter \geq 5mm, fistula flow \geq 500 mL/min. If radiographic maturation has been achieved before the 150-day follow-up visit, the subject will not switch to the Post Maturation follow-up schedule until the 150 Day visit when the EchoSure scans are suspended. Post-Maturation follow-up visits will include a physical exam, medical history review, Duplex scan, external EchoMark measurement, and adverse event monitoring. The physical exam will include assessing the fistula for bruit and thrill. The medical history will include all interventions, cannulation attempts, and the most recent Kt/V, CBC, Serum Chemistry, Calcium, Phosphorous, Magnesium, Total Protein, Albumin, PTH, Duplex scans will include:

• Assessment of patency (flow/no flow adjudicated by the CEC)

- Limited DUS scan performed at the site of EchoMark to determine EchoMark visibility including:
 - o 1 BMode, transverse view of EchoMark at center
 - o 1 BMode, transverse view of EchoMark at distal edge
 - o 1 BMode, Transverse view of EchoMark at proximal edge
 - 1 BMode, Longitudinal view centered over vessel showing full length of EchoMark
- A duplex exam of the fistula from the EchoMark location and beyond to assess for the presence of stenotic lesions. If a lesion is present, capture and save an image showing a longitudinal view of the fistula segment with the stenosis, note the location of the stenosis in relation to the anastomosis and EchoMark, and track the stenosis as an adverse event.
- A duplex scan of the brachial artery to assess flow and diameter, capture a PW image showing the flow and diameter measurements.

7.8 180 Day and 12 Month (+ 15 Days) Follow-up

All subjects will have follow-up visit at 180 days and 12 months after baseline procedure. Follow-up visits will include a physical exam, medical history review, Duplex scan, external EchoMark measurement, and adverse event monitoring. The physical exam will include assessing the fistula for bruit and thrill. The medical history will include all interventions, cannulation attempts, and the most recent Kt/V, CBC, Serum Chemistry, Calcium, Phosphorous, Magnesium, Total Protein, Albumin, PTH, Duplex scans will include:

- Assessment of patency (flow/no flow adjudicated by the CEC)
- Limited DUS scan performed at the site of EchoMark to determine EchoMark visibility including:
 - 1 BMode, transverse view of EchoMark at center
 - 1 BMode, transverse view of EchoMark at distal edge
 - 1 BMode, Transverse view of EchoMark at proximal edge
 - 1 BMode, Longitudinal view centered over vessel showing full length of EchoMark.
- A duplex exam of the fistula from the EchoMark location and beyond to assess for the presence of stenotic lesions or a fluid collection. If a lesion is present, capture and save an image showing a longitudinal view of the fistula segment with the stenosis, note the location of the stenosis in relation to the anastomosis and EchoMark, and track the stenosis as an adverse event. If a fluid collection is present, capture and save an image noting the location from the anastomosis and the size and volume.
- A duplex scan of the brachial artery to assess flow and diameter, capture a PW image showing the flow and diameter measurements.

7.9 15 Month, 18 Month, and 24 Month (+ 15 Days) Follow-up

All subjects who are willing to reconsent to longer-term follow-up will have a follow-up visit at 15 months, 18 months, and 24 months after baseline procedure. Follow-up visits will include a captures of medical history since the last visit, Duplex scan, and adverse event monitoring. The Duplex scans will include:

- Limited DUS scan performed at the site of EchoMark to determine EchoMark visibility including:
 - 1 BMode, transverse view of EchoMark at center
 - 1 BMode, transverse view of EchoMark at distal edge
 - o 1 BMode, Transverse view of EchoMark at proximal edge
 - 1 BMode, Longitudinal view centered over vessel showing full length of EchoMark
- A duplex exam of the fistula from the EchoMark location and beyond to assess for the presence of a fluid collection. If a fluid collection is present, capture and save an image noting the location from the anastomosis and the size and volume.

7.10 Fistula Outside of the EchoMark

If the subject's fistula is deemed to be outside of the EchoMark, an adverse event form will be completed and adjudicated by the CEC. The subject will remain in the study. The EchoSure scans will be suspended. The subject will complete the follow-up schedule as scheduled. Each follow-up visits will include a physical exam, medical history review, Duplex scan, external EchoMark measurement, and adverse event monitoring. The physical exam will include assessing the fistula for bruit and thrill. The medical history will include all interventions, cannulation attempts, and the most recent Kt/V, CBC, Serum Chemistry, Calcium, Phosphorous, Magnesium, Total Protein, Albumin, PTH, Duplex scans will include:

- Depth, Diameter and Volume Flow at/near the EchoMark
- Assessment of patency (flow/no flow adjudicated by the CEC)
- Limited DUS scan performed at the site of EchoMark to determine EchoMark visibility including:
 - 1 BMode, transverse view of EchoMark at center
 - o 1 BMode, transverse view of EchoMark at distal edge
 - 1 BMode, Transverse view of EchoMark at proximal edge
 - 1 BMode, Longitudinal view centered over vessel showing full length of EchoMark
- A duplex exam of the fistula from the EchoMark location and beyond to assess for the presence of stenotic lesions. If a lesion is present, capture and save an image showing a longitudinal view of the fistula segment with the stenosis, note the location of the stenosis in relation to the anastomosis and EchoMark, and track the stenosis as an adverse event.
- A duplex scan of the brachial artery to assess flow and diameter, capture a PW image showing the flow and diameter measurements.

The subject will follow the same 180-day and 12-month visit follow-up visit as described in Section 7.8 7.8 180 Day and 12 Month (+ 15 Days) Follow-up

7.11 Fistula Failure

If the subject's fistula is deemed a failure and abandoned by the investigator, a fistula failure case report form will be completed recording the reasoning for the failure. The subject will remain in the study and receive monthly telephone calls to monitor for adverse events and physical assessments of the EchoMark at all standard of care visits. The subject will complete the 180-day and 12 months visit as scheduled to undergo a physical exam, medical history review, adverse event monitoring, and duplex examination of the EchoMark and exit the study.

7.12 EchoMark Explantation

If the EchoMark is removed, the subject will be followed until the event is resolved. A case report form will be completed to track the reasoning, procedure details, and outcomes. The subject will be monitored with the institution's standard of care, including physical exam and possibly ultrasound. The event will be tracked until the symptoms are resolved and the subject will exit the study.

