9.5 Event Assessment and Follow-Up

The occurrence of an adverse event (AE) or serious adverse event (SAE) may come to the attention of study personnel during study visits and interviews of a study participant presenting for medical care, or upon review by a study monitor.

All AEs including local and systemic reactions not meeting the criteria for SAEs will be captured on the appropriate case report form (CRF). Information to be collected includes event description, time of onset, clinician's assessment of severity, relationship to study product, and time of resolution/stabilization of the event. All AEs occurring while on study must be documented appropriately regardless of relationship. All AEs will be followed to adequate resolution.

Any medical condition that is present at the time that the participant is screened will be considered as baseline and not reported as an AE. However, if the study participant's condition deteriorates at any time during the study, it will be recorded as an AE.

Changes in the severity of an AE will be documented to allow an assessment of the duration of the event at each level of severity to be performed. AEs characterized as intermittent require documentation of onset and duration of each episode.

Investigators will record all reportable events with start dates occurring any time after informed consent is obtained until 7 (for non-serious AEs) or 30 days (for SAEs) after the last day of study participation. At study visits, the investigator will inquire about the occurrence of AE/SAEs since the last visit. Events will be followed for outcome information until resolution or stabilization.

The Investigator is to report all SAEs to the study sponsor within 24 hours of first recognition of the event. Additionally, any device malfunctions, failures, and/or explants are to be reported to the sponsor within 24 hours of first recognition of the event.

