11.2.8.11 Composite of new major device related adverse events (MAEs) at 12 months

The proportion of subjects with device success and free from deviceand/or procedure-related SAEs (per CEC adjudication) at 12 months. The summaries for each individual safety data point will also be provided. Composite of new major device related adverse events (MAEs) at 12 months post EchoMark LP implantation, as adjudicated by the Clinical Events Committee (CEC), including:

- Device or procedure-related death
- Device related infection
- Device related interventions
- Device related hospitalizations
- Fistula failure
- Fistula rupture
- Aneurysm

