11.2.10 Handling of Missing Data

Data will only be absent from analyses of study outcomes in the event that they were not available for collection. In general, missing values in any of the endpoints will not be inputted when summarizing these endpoints using descriptive statistics.

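### Subjects leave the study once symptoms resolve after EchoMark explantation, so their later patency, maturation and adverse events go unobserved, and no rule says how to count them

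*Combined protocol and SAP*

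**What the plan says.** Section 7.12 follows an explanted subject only until the event is over: "The event will be tracked until the symptoms are resolved and the subject will exit the study". Before that, "A case report form will be completed to track the reasoning, procedure details, and outcomes". It asks for no contact at 180 days or 12 months.

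The neighbouring rules differ. Section 7.8 gives every subject a 180-day and a 12-month visit. Section 7.10 keeps a subject whose fistula lies outside the EchoMark on the visit schedule and stops only the EchoSure scans. Section 7.11, on fistula failure, says "The subject will remain in the study and receive monthly telephone calls to monitor for adverse events" and requires the 180-day and 12-month visits before exit.

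On event capture, Section 9.5 requires that "any device malfunctions, failures, and/or explants are to be reported to the sponsor within 24 hours", and it collects events "until 7 (for non-serious AEs) or 30 days (for SAEs) after the last day of study participation". Under Section 12.7 the CEC adjudicates every reported event.

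On analysis, Section 11.2.4 takes all subjects with a successful implantation, and Section 11.2.1 uses all available data. Section 11.2.10 adds that "missing values in any of the endpoints will not be inputted when summarizing these endpoints using descriptive statistics" (evidently meaning imputed). Section 11.2.8.11 summarises "The proportion of subjects with device success and free from deviceand/or procedure-related SAEs (per CEC adjudication) at 12 months", along with the components of the MAE composite. Sections 11.2.8.7 and 11.2.8.8 define patency as a status at 6 and 12 months, conditional on both maturation definitions being met. No section says how a subject who exits after an explant enters any of these summaries.

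**The concern.** Device removal is the only one of the three departures from the normal course (fistula outside the marker, fistula failure, explantation) that ends observation, and the plan gives no reason for the difference. Section 8 links removal to signs of infection, inflammation or extrusion, and it reports infection and seroma in earlier use in this population. Exit is therefore a consequence of the device outcomes under study, and the data lost by it cannot be treated as missing at random.

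The information at stake is what happens after the device is taken out: whether the access stays patent, whether it matures, and whether further events follow. Under an available-case summary, the later time points would mainly describe subjects who kept the device. With up to 20 subjects, and no replacement of those who leave after implantation (Section 10.2), each subject is worth 5 percentage points.

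**Working it through.** There is no plan figure to reproduce. Section 11.1 states no hypothesis, and the documents give no explant rate and no expected patency rate for this study.

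**Step 1: what is kept.** An explant happens before exit. It goes on a case report form (7.12), to the sponsor within 24 hours (9.5) and to the CEC (12.7). Device-related interventions and device-related infection are components of the 30-day and 12-month composites (4.2.1, 11.2.8.11). Explantation is also written into one of the infection endpoints in 11.2.8.10. The event that triggers the exit is therefore not lost.

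**Step 2: how far event collection reaches.** Let E be the exit day, counted from implantation. Under Section 9.5, serious events are collected to day E + 30 and non-serious events to day E + 7.

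- Day 30, serious: E + 30 ≥ 30 holds for every E ≥ 0, so coverage is complete.
- Day 30, non-serious: E + 7 ≥ 30 requires E ≥ 23. After an earlier exit, a new non-serious MAE component (the composite does not require infection, fistula failure or aneurysm to be serious) goes uncollected if it starts more than 7 days after exit.
- 12 months (day 365), serious: E + 30 ≥ 365 requires E ≥ 335.
- 12 months, non-serious: E + 7 ≥ 365 requires E ≥ 358.

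For most exit dates, then, the 12-month event counts and component summaries are cut short for these subjects.

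**Step 3: status endpoints.** Patency at 6 or 12 months needs an assessment at that time. After an earlier exit the value is missing and Section 11.2.10 leaves it missing. The same holds for maturation not reached by the exit date.

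**Step 4: illustration for 12-month patency.** All of the following is assumed: N = 20 implanted subjects (roll-ins left aside), all meeting the maturation condition; k explanted subjects who exit before 12 months; f patency failures among the others.

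- Available-case rate = (N − k − f)/(N − k)
- Lower bound, no explanted subject patent = (N − k − f)/N
- Upper bound, all explanted subjects patent = (N − f)/N

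| f | k | Available-case | Lower bound | Upper bound |
|---|---|---|---|---|
| 2 | 1 | 17/19 = 89.5% | 17/20 = 85.0% | 18/20 = 90.0% |
| 2 | 2 | 16/18 = 88.9% | 16/20 = 80.0% | 18/20 = 90.0% |
| 2 | 3 | 15/17 = 88.2% | 15/20 = 75.0% | 18/20 = 90.0% |
| 4 | 2 | 14/18 = 77.8% | 14/20 = 70.0% | 16/20 = 80.0% |

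For f = 2 and k = 2, the available-case figure can be too high by up to 88.9 − 80.0 = 8.9 points, or too low by up to 90.0 − 88.9 = 1.1 points. It behaves as if explanted subjects had the same patency as everyone else, which is hard to defend when removal followed a device complication.

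**The case against.** The strongest reply is that the plan does not discard bad device outcomes. A reader might infer that the safety rates are computed without explanted subjects. The documents do not support this. The explant is recorded before exit, the analysis sample is everyone implanted, all available data are used, and a related explant fits named composite components. Leaving such a subject out would go against Sections 11.2.1 and 11.2.4. This part of the reply stands.

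A reader might also infer that the 30-day safety result is compromised. For serious events it is not, since collection always reaches day 30 (Step 2). The residue is narrow: a non-serious component starting more than 7 days after an exit before day 23. It affects the component summaries, and the composite only where the explant itself was not counted.

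Third, removing the marker does not mean losing the fistula. If the explanted subjects stayed patent, the available-case rate is slightly too low, so a bias in the device's favour cannot be asserted for patency. That stands too; the figures above are bounds.

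Fourth, the maturation condition in Sections 11.2.8.7 and 11.2.8.8 may remove some explanted subjects from the patency rate whatever Section 7.12 says. This is true, but whether the condition was met may itself depend on data after exit.

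Finally, Section 7.12 can be read as a specific exception to Section 7.8, and Section 7.11 is an imperfect parallel because there the marker is still in place. Reading it as an exception removes the contradiction but not the data loss, and the telephone contacts in Section 7.11 show that such follow-up is feasible in this study.

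**Conclusion.** The point holds for outcomes after the explant, not for the explant itself. Section 7.12 conflicts with Section 7.8 and with the retention rules in Sections 7.10 and 7.11. As written, it leaves 6- and 12-month patency, maturation not yet reached, and later events unobserved and not imputed, for a reason tied to the device. Under the assumed 20 subjects, 2 explants and 2 other failures, reported 12-month patency of 88.9% would stand for a possible range of 80.0% to 90.0%. The number of explants is an assumption, and the direction of any patency bias is not established.

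For the composites, what remains is ambiguity. Device success and evaluable are not defined, the denominator is not stated, and Section 9.1 leaves it to judgement whether an event needing surgery is serious. A related explant could thus be a composite component without breaking freedom from serious events. A counting rule would close this gap. The study is descriptive and no test depends on these rates, so this is a cheap improvement and does not threaten the design.

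**What to change.** 1. In Section 7.12, replace the study exit with data collection only, with no change in care: adverse event status, access patency and maturation status, from records or by telephone, at the remaining scheduled time points through 12 months. Reconcile the section with Sections 7.8 and 7.11. The patency definition in Section 4.2.3 rests on imaging or physical examination, so a telephone report should be backed by a documented finding where one exists.
2. In Sections 11.2.6 and 11.2.8.11, state that explants the CEC adjudicates as device- or procedure-related count as events, with all implanted subjects in the denominator. Explants adjudicated as unrelated should not count automatically, since that would change what the composite measures.
3. In Sections 11.2.8.7 and 11.2.8.8, keep explanted subjects who met the maturation condition in the denominator. Where their status is unknown, report the rate with all of them patent and with none of them patent, beside the available-case figure.

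The cost is a few extra contacts or record requests for what is likely to be a handful of subjects, plus a few sentences in the analysis plan. No extra procedure is needed. Some rates may come out slightly less favourable.
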